10.3 POPULATIONS FOR ANALYSES

An intent-to-treat (ITT) population will be defined as all adult patients whose trachea was intubated with either a EVAC-PU-ETT or PVC-ETT from one of the study kits and admitted to any adult Intensive Care Unit (ICU). Approximately 1,074 patients will be included.

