1) Patients electively intubated in the operating room whether or not they require subsequent ICU admission; 2) Use of a non-study intubation kit (such as nasal intubation, tracheotomy, intubation occurring at a location not supplied with the study intubation kits); 3) Patients with permanent tracheostomy; 4) Protected populations including children (age <18 years), pregnant women, prisoners; and 5) Evidence of unwillingness to participate in a research study as documented in the patient's electronic health record, or at the time of intubation if there is opportunity to read the opt-out script.

Phase:	2
Site/Facility:	The study will be conducted at a single site. The first 90 patients were enrolled at Oregon Health & Science University (OHSU), the subsequent 984 subjects will be enrolled at Yale New Haven Hospital (YNHH), a non-profit 1,541-bed hospital and tertiary referral center for critically ill patients in the region with four intensive care units and emergency department. YNHH is a nationally recognized biomedical research institution with adequate administrative core resources to enable start-up processes of post-award facilitation and ethics board review as well as smooth facilitation of study processes.
Description of Study Intervention:	The study ETTs (EVAC-PU-ETT and PVC-ETT) will be concealed and packaged in an opaque sealed envelope so that the assignment will occur in a blinded fashion. The study ETTs will be provided in three internal diameter sizes: 7.0 mm, 7.5 mm, and 8.0 mm. Unless otherwise indicated, the size recommendation will be I.D. 7.0 for females, I.D. 7.5 for males, and I.D. 8.0 as clinically indicated. Non-study ETT will be also available for use in protected populations, and for patients with exclusion criteria, and for participants declining consent. Also, if a study device becomes unusable at the time of intubation, non-study ETT would be available as replacement for the study ETT. The intubation kits will be distributed by research personnel to Anesthesia, ICUs, and ED storage locations. Study device packaging will be tracked using a barcode system.
Study Duration:	The proposed enrollment period is 15 months, with an additional 6 months to ensure that all participants complete the follow up. The duration of enrollment assumes 40% losses from ineligibility and exclusions.

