It may be difficult to differentiate side effects of the ETT from complications patients who undergo intubation experience regardless of the type of ETT used. The product labels for both ETTs show no differences in the type, nature, or severity of complications between the tube types. Device-related complications are considered the same. Some subjects will receive the EVAC-PU-ETT and they would not otherwise receive this ETT type outside of the study. However, both ETTs we will use are medically recognized standards of care and there is no known differential in risk between the two treatments.

From clinical experience, it is expected that the EVAC-PU-ETT is as safe as the PVC-ETT. For these reasons, we believe that subjects enrolled in this study will be exposed to the same risks if they were outside of the study.

This study will specifically evaluate the following immediate, short, and long-term device-related complications involving laryngeal anatomy and function that are also outlined in the product labeling:

Immediate risks:

- Airway complications at the time of tube insertion
- Need to change/reduce the pre-assigned size of the tube

Short-term risks:

- Stridor immediately after extubation
- Requirement for stridor treatment
- Reintubation within 24 hours due to upper airway complications such as stridor or obstruction

Long-term risks (6 months after extubation as identified by a phone interview)

- Tracheostomy
- Persistent throat discomfort or pain
- Stridor
- Residual hoarseness or change in voice (dysphonia)
- Dyspnea
- Whether dyspnea symptoms are attributable to upper or lower airway disease (certainly due to upper airway, probably, possibly, or unrelated).

Section 9.2 outlines how the study team will assess airway complications for safety of the ETT type during the study.

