We do not expect differences in risks at insertion between the PVC-ETT and the EVAC-PU-ETT. However, while the tubes have the same internal diameter, the EVAC-PU-ETT tube has a slightly larger external diameter (due to the additional port) which effectively increase the outer diameter by 0.5 points. This may mean a different tube is requested prior to the intubation attempt or it is requested after a failed attempt is made. If this happens because the outer diameter of the tube is thought to be a problem, a non-study tube will be used. Specifically, if a <7.0 size is needed, then it will not be a study tube since alternative sizes are not available for this study. We will monitor insertion complications, including the need to insert smaller size tubes.

Complications related to mechanical ventilation are not research risks and are instead due to standard of care which subjects would be exposed to outside of the study. However, certain symptoms, like dyspnea, will not be distinguishable between device and ventilator. Assessment of risks will primarily focus on complications to upper airway which are more closely related to the breathing device than the ventilator use. For the trial, we will document whether the symptoms are thought to be related to upper vs lower airway dysfunction (evidence of pulmonary disease or condition), and we will compare the frequency between the two groups.

This study will evaluate cognitive function. We do not expect cognitive changes to represent side effects of the ETT. We hypothesize that decreased cognitive function is a consequence of infection (VAP) as a result of neuroinflammation. We hypothesize that patients that do not experience infection or hypoxemia resulting from pneumonia should have less cognitive dysfunction. If the EVAC-PU-ETT is protective from VAP, then the intervention group should also have less cognitive dysfunction. Therefore, side effects of cognitive dysfunction are not research risks, and are instead risks of the condition they would be exposed to outside of the study.

This study increases the risk of invasion of privacy as patients will be enrolled into this emergency medicine study without his or her consent. We anticipate most subjects will be enrolled in the study under a waiver of consent because this patient population may not immediately have the capacity to provide consent to be in the study.

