7.1.2 RANDOMIZATION

Because endotracheal intubation is performed in an emergency setting, the unit of randomization will be the intubation kits containing, in a concealed manner, either a PVC-ETT or EVAC-PU-ETT, assigned in a random and equal fashion. Both the opaque envelope and the study ETTs stored within will be labeled using a barcode system linked to the randomization number for identification and tracking.

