7.3 MEASURES TO MINIMIZE BIAS: RANDOMIZATION AND BLINDING

All possible measures to reduce bias due to the choice of the device have been taken by blinding caregivers to the treatment assignment ahead of time via concealment of the study tube in an opaque sealed envelope. However, double blinding cannot be maintained for the entire duration of the study because the study devices are visibly different. We realize that lack of double blinding could lead to the potential for bias. However, determination of primary and many secondary outcome measures and statistical analyses will be performed without knowledge of device assignment. Importantly, we have chosen objective measures for the primary and secondary endpoints, and standardized the way procedures are performed, thus removing subjectivity and variability. Crossovers will be minimized by maintaining a spare ETT of the same model and size at the bedside during the ICU stay, up to 24 hours after extubation or until ICU discharge, whichever comes first. If crossovers occur, the study will follow an intention-to-treat approach. There will be situations when patients will be diagnosed with pneumonia using clinical criteria or in the absence of respiratory cultures. In secondary analyses, we will evaluate a “clinical” diagnosis of VAP and respiratory antimicrobial use as endpoints.

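### Does the Section 10.3 intent-to-treat set need to be redefined because it admits only patients in whom a study-kit tube was placed?

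*Combined protocol and SAP*

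**What the plan says.** Section 10.3 defines the intent-to-treat population as "all adult patients whose trachea was intubated with either a EVAC-PU-ETT or PVC-ETT from one of the study kits", with admission to an adult ICU as a further condition. Section 7.1.2 says that "the unit of randomization will be the intubation kits containing, in a concealed manner, either a PVC-ETT or EVAC-PU-ETT". Section 7.3 explains that blinding cannot last "because the study devices are visibly different".

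Section 3.3.1 notes that the EVAC-PU-ETT has the slightly larger outer diameter. It continues: "This may mean a different tube is requested prior to the intubation attempt or it is requested after a failed attempt is made". Then: "If this happens because the outer diameter of the tube is thought to be a problem, a non-study tube will be used". The next sentence of that section narrows this to patients who need a size below 7.0, which the study does not supply. The Synopsis gives a second route out: "if a study device becomes unusable at the time of intubation, non-study ETT would be available as replacement for the study ETT".

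On recording, Section 3.3.1 lists among the immediate risks "Need to change/reduce the pre-assigned size of the tube" and states: "We will monitor insertion complications, including the need to insert smaller size tubes". Sections 7.1.1, 7.2.1 and 7.2.2 have used kits returned, scanned and reconciled, with a barcode tied to the assignment. Sections 10.4.4 and 10.4.5 do not ask for a table, by arm, of kits that were opened but whose tube was not placed.

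**The concern.** An intent-to-treat set should not depend on anything that happens after the assignment can be known. Here the assignment is exposed when the envelope is opened, and placement comes afterwards. The protocol names a reason for abandoning the study tube that belongs to one arm, the wider EVAC tube. If patients with difficult airways left the EVAC arm more often than the PVC arm, the remaining EVAC patients would look healthier than those assigned, and a non-inferiority conclusion on laryngeal injury (margin 0.05) would come too easily. The rule in Section 7.3 that crossovers are analysed by intention to treat covers patients already in the set, not those who never join it. The sensitivity analyses under Missing Data in Section 10.2 concern missing outcomes, not this selection. A reader who sees the label intent-to-treat would have no cue to look for it.

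**Working it through.** **The plan's own figure.** Section 10.3 expects about 1,074 patients, the size set in Section 10.2: 2 × 537 = 1,074. For a difference of 0.17 SD at two-sided 5%, power = Φ(0.17/√(2/537) − 1.96) = Φ(0.826) = 0.795, against 80% stated. The figure reproduces and does not depend on how the set is labelled.

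**How a patient can leave the set.**

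| Place | What it implies |
|---|---|
| Section 9.1 | randomisation and device placement are described as one step |
| Section 2.3 | randomisation assignment falls under the study-tube placement column |
| Section 6.2, criterion 2 | use of a non-study kit is an exclusion |
| Section 7.1.1 | staff confirm at the bedside that a study device was inserted |
| Section 7.2.4 | each kit holds 7.0, 7.5 and 8.0 of one tube type |
| Section 3.3.1 | a size below 7.0 is never a study tube |

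Read together, these make placement the event that brings a patient into the trial. A clinician who moves to a smaller tube in the same kit keeps the patient in the set and in the assigned arm. The remaining exits are mainly a need for a size below 7.0 and an unusable device. A switch requested before the envelope is opened is blind to arm and cannot bias the comparison.

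**Size of the possible bias.** The documents give no loss rate and no injury risk for patients whose kit was opened but not placed, so every value of x and r below is an assumption. Let p be the risk among all assigned, x the fraction lost and r the risk in those lost, the same in both arms. The risk seen in the placed set is (p − x·r)/(1 − x).

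With p = 0.39 in both arms (the pilot PVC value in Section 10.4.2), x = 0.02 EVAC and 0.01 PVC:

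- r = 0.2: 0.3939 − 0.3919 = +0.002
- r = 0.39: 0
- r = 0.8: 0.3816 − 0.3859 = −0.004

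With x = 0.05 and 0.01: +0.008 at r = 0.2 and −0.017 at r = 0.8.

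**Error at the margin.** Take true risks of 0.44 and 0.39, 537 placed per arm, one look at one-sided 0.025, and an SE of about 0.030. The error is Φ((0.05 − d)/SE − 1.96), where d is the difference in the placed set.

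| Lost, EVAC v PVC | r = 0.2 | r = 0.39 | r = 0.6 | r = 0.8 |
|---|---|---|---|---|
| 2% v 1% | 0.020 | 0.023 | 0.027 | 0.032 |
| 5% v 2% | 0.012 | 0.020 | 0.034 | 0.054 |
| 5% v 1% | 0.010 | 0.020 | 0.040 | 0.071 |

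If only EVAC kits were lost, with r from 0.6 to 0.8, the error would be 0.032 to 0.043 at 2% lost and 0.047 to 0.092 at 5% lost.

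Each row of the table lies on both sides of 0.025. Those lost may be at higher risk (difficult airway) or at lower risk (no lasting exposure to the study tube), so the sign is not known.

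**What a sensitivity analysis would add.** Suppose 11 EVAC and 5 PVC patients were unplaced (11/548 = 2.0%, 5/542 = 0.9%) and placed patients showed 0.39 in both arms. Arm risk = (537 × 0.39 + m·r)/(537 + m), where m is the number unplaced.

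- r = 0.8 EVAC, 0.2 PVC: 0.3982 − 0.3882 = +0.010
- r = 0.2 EVAC, 0.8 PVC: 0.3862 − 0.3938 = −0.008

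The protocol provides no six-month visit for patients who are never enrolled, so this range would come almost wholly from the assumed r.

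**The case for a change.** The strongest case for a change is that the text, taken literally, is not intent-to-treat. The kit is randomised, a failed attempt with a study tube must come after opening, and Section 10.3 then drops that patient for a reason tied to one arm. Reading placement as randomisation moves the date of randomisation but does not remove selection after the tube has been seen. Section 3.2 faults earlier subglottic-suction trials for post-randomisation exclusions, so the same standard can fairly be applied here. At 5% loss confined to the EVAC arm the one-sided error could nearly quadruple (0.092 against 0.025), and only a count by arm can tell that case from a harmless one.

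Much of this stands. The label is loose: the set also depends on ICU admission, and Section 8.2 removes inadvertent enrolments with their data. The text does not say outright how to class a failed study-tube attempt followed by a non-study tube. Inclusion criterion 3 asks that a kit was used, whereas Section 10.3 asks for intubation with its tube, although the natural reading of the criterion agrees with Section 10.3.

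What does not stand is the step from possible selection to a rule that gives a wrong result. The large figures need a 5% loss that the documents do not suggest. Section 3.3.1 calls the diameter difference slight and expects no difference in insertion risk.

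**Conclusion.** This is a gap that analysts fill sensibly, and no change to the plan is needed. The set in Section 10.3 is patients with a study tube placed and admitted to an ICU, compared by assigned kit, whatever it is called. Renaming it would leave the primary test, its population and its power as they are. The one useful extra is the number of kits opened but not placed, by arm and with reasons. That belongs in the participant flow and can be drawn from the barcode reconciliation already planned, although returns may be incomplete. Section 9.1 also records laryngoscopy attempts, Section 7.4 records technical tube problems, and Section 10.4.5 compares baseline by arm, which is a weak check at low loss rates. A sensitivity analysis on patients who were never enrolled would rest on assumed outcomes and add little.

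The size is small under the assumption that few kits are lost after opening: at 2% v 1%, a shift of at most 0.004 against a margin of 0.05, and an error between 0.020 and 0.032. The conclusion rests on that assumption and on reading placement as the point of randomisation. If the flow counts showed about 5% or more lost in one arm, the safety result would need a caveat when reported.

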10.4 STATISTICAL ANALYSES

10.4.1 GENERAL APPROACH

The statistical analysis plan (SAP) for the final statistical report contains the planned analyses indicated in the study protocol.

10.4.2 ANALYSIS OF THE PRIMARY EFFICACY ENDPOINT(S)

Analysis of Safety Primary Endpoint

One objective of this study is to establish that the experimental treatment, EVAC-PU-ETT, has a safety profile that is not inferior to the standard treatment, PVC-ETT. For this aim, we will conduct a non-inferiority analysis and test that the underlying population risk of laryngeal injury for the EVAC-PU-ETT treatment group is not statistically higher than the population risk of laryngeal injury for the PVC-ETT treatment group. To evaluate the non-inferiority of laryngeal risk of the EVAC-PU-ETT treatment, we specify a non-inferiority bound that the difference in the true risk probabilities is less than or equal to 0.05. That is, $q = p_1 - p_0 < 0.05$, where p_1 denotes the risk of laryngeal injury for the EVAC-PU-ETT treatment group, p_0 denotes the risk of laryngeal injury for the PVC-ETT treatment group and therefore,

q , denotes the difference in the two risk probabilities. The test of hypothesis for the primary endpoint is a two-sample difference in risk in a group sequential design with one planned interim analysis. The analysis will be conducted when approximately 50 percent of the total sample has been collected. The group sequential stopping rule is based on 2.5 percent significance level and a one-sided stopping rule with an O'Brien-Fleming boundary. The interim analysis would take place when approximately 537 (269 patients per study arm) have been accrued. At the time of the interim analysis, the trial would be stopped if the estimated risk difference, $p_1 - p_0$, is greater than the safety boundary of 0.0956, indicating EVAC-PU-ETT is significantly more harmful than PVC-ETT. Evaluation of the estimated differences will be obtained using standard, fixed-sample maximum likelihood estimates (MLEs). The MLEs provide valid point estimates for evaluating the group sequential design stopping rules. At the conclusion of the study, the estimated difference, confidence intervals and associated p-values require adjustment, accounting for the interim analyses. We consider bias adjusted estimates ⁴ and Rao-Blackwell adjusted estimates ⁵ to correct for the bias in the fixed sample MLEs. Sample mean ordering ⁵ will be used to adjust confidence intervals and p-values.

Specifically, we will evaluate whether there is a difference in the laryngeal injury risk probabilities for the two treatments, we will use maximum likelihood estimation (binomial family) with an identity link function. The statistical model used for this analysis will be: $p(X) = \beta_0 + \beta_1 X$ where $p(X)$ denotes the laryngeal injury probability and X is an indicator denoting the treatment assignment (1 = EVAC-PU-ETT, 0 = PVC-ETT). The identity link function makes the interpretation of parameter for the treatment effect, β_1 , be equal to $\beta_1 = p(1) - p(0)$, which is exactly the risk difference, q , noted above. In the Prevent pilot study, the estimated risk of laryngeal injury was 0.39 for the PVC-ETT treatment group and 0.38 for the EVAC-PU-ETT treatment group. Assuming an estimated risk difference less than or equal to 0.05 for the targeted sample size of $N=1074$ (537 patients per treatment arm) for the pre-specified alpha-level and statistical design, the statistical power for concluding non-inferiority of the EVAC-PU-ETT treatment group would be 80 percent.

Analysis of Quality of Life Primary Endpoint

We will evaluate whether there are differences in quality of life measures between treatment groups by comparing mean scores. Separate analyses will be conducted for the two endpoints. The statistical model will be linear regression, $\mu(X) = \beta_0 + \beta_1 X$, where $\mu(X)$ denotes the mean SF-36 score, X is an indicator denoting the treatment assignment as before. The test for a treatment effect is denoted by, $\beta_1 = \mu(1) - \mu(0)$. We will use robust inference so that our tests will be valid for modest departures in modeling assumption. Additionally, we will transform the scores to reflect “percent of healthy life”. This transformation of the SF-36 measures provides easily interpretable variables and allow for the retention of patients that die during the study. As noted previously, the design for this endpoint is a fixed sample design. To have power of at least 80 percent for the targeted sample size of $N=1074$, we require a difference in the means to be greater than 0.17 standard deviations on a standardized scale. These

power and effect size calculations assume an independent, two-sample test, an alpha level of five percent and all statistical tests are two-sided tests.

Analysis of Cognitive Impairment Primary Endpoint

To evaluate whether there is a difference in the risk of cognitive impairment between the two treatments, we will use the same fixed sample methods used for the primary safety endpoint. We will estimate the difference in the probability of cognitive impairment for the two treatments using maximum likelihood estimation (binomial family) with an identity link. We will use robust (sandwich) standard error estimates in the test statistics and confidence intervals to remedy possible minor violations of modeling assumptions. The design for this endpoint is a fixed sample design. We assumed a prevalence of cognitive impairment of 0.40 for this at population, a sample size of N=1074, we require a minimum risk difference of 0.09 ($q = p_1 - p_0 < -0.09$) to attain statistical power of at least 80 percent. We assumed a prevalence of cognitive impairment of 0.40, however, the risk difference of 0.09 attains the targeted level of power or higher, for a prevalence in a reasonable range (e.g., 0.2-0.8).

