Surveillance for VAP will occur while patients are in the ICU until extubation, ICU discharge or death. A large proportion of patients is expected to be extubated within 48 hours. Although patients with early extubation are not considered to be at risk of VAP, they will be included in the study to adhere to the intent-to-treat approach, considering that the patient has been randomly assigned to one of the study treatment arms. Throughout the patient's hospitalization, data will be collected continuously from the time of randomization until hospital discharge or death.

The study will use clinical measures to address device safety and consequences of VAP reduction on long-term, patient-centered outcomes. At six months post randomization, all patients will have a structured in-person interview to screen for the presence of and assess airway symptoms or persistent sequelae of laryngeal dysfunction. Any need for consultation of a specialist for airway complaints will be recorded and information abstracted from the medical record, if appropriate. During the interview, we will record clinical measures intended to evaluate safety, quality of life, and cognitive function. If a visit

to a specialist for evaluation and/or treatment of speech, swallowing, or breathing problems occurred, the medical record will be reviewed. Data pertinent to the continuing adverse event will be abstracted from the medical record.

Although randomization assignment occurs in a double-blind fashion, the study will subsequently be single-blind. Due to the different devices used and the presence of suctioning, it will not be possible to maintain the study as double-blind. To protect the integrity of the study from unmasking of investigators other than the primary caregivers, the adjudication of the VAP will follow an algorithmic, data-driven, objective approach. Likewise, the follow up airway assessment will occur in a blinded fashion. The statistician will be blinded to the randomization assignment, by labeling the randomization assignment as device A or B.

One interim analysis will be conducted when approximately 50 percent of the total sample has been collected. For details on planned interim analyses see **Section 9.4.6, Planned Interim Analysis**.

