10 STATISTICAL CONSIDERATIONS

10.1 STATISTICAL HYPOTHESES

Our central hypothesis is that EVAC-PU-ETT is as safe as the standard PVC-ETT and is superior to the standard PVC-ETT in reducing the occurrence of VAP and several of its long-term consequences.

The primary objectives of the proposed trial are to compare the clinical safety and effectiveness of EVAC-PU-ETT compared with PVC-ETT. The primary clinical endpoints will be: safety, quality of life, and cognitive impairment. Safety, measured as long-term laryngeal injury, will be tested for equivalence between the two treatment groups, or more precisely, that the EVAC-PU-ETT treatment is “non-inferior” to the PVC-ETT treatment. Quality of life will be assessed using the RAND Short Form Health Survey (SF-36) Physical Component Summary (PCS) and Mental Component Summary (MCS). For cognitive impairment, patients will be considered cognitively impaired if their global cognition scores are at least 1.5 standard deviation (SD) below the population mean (for comparable patients with moderate TBI) in at least two global cognition scores or more than 2 SD below the population mean for a single global cognition score. Safety will be analyzed using a sequential design with one interim analysis. The primary aims for quality of life and cognitive impairment will be evaluated for superiority of the EVAC-PU-ETT treatment using a fixed sample design. The treatment effect will be measured as the difference in probability risks, between the treatment groups, for the safety and cognitive impairment outcomes. The

treatment effect for the quantitative quality of life outcomes will be represented as differences in means.

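### The fixed interim harm boundary of 0.0956 does not match its one-sided 2.5% O'Brien-Fleming label at the only laryngeal-injury risks the plan gives, and the plan leaves open how many patients must have the outcome at the look

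*Combined protocol and SAP*

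**What the plan says.** Section 10.4.2 (Analysis of Safety Primary Endpoint) tests laryngeal injury for non-inferiority with a margin of 0.05 and one interim look. On the rule it says: "The group sequential stopping rule is based on 2.5 percent significance level and a one-sided stopping rule", with an O'Brien-Fleming shape. The trial stops if the estimated risk difference, EVAC-PU-ETT minus PVC-ETT, "is greater than the safety boundary of 0.0956, indicating EVAC-PU-ETT is significantly more harmful than PVC-ETT". No risk or variance is given for that number. The only laryngeal-injury risks in the plan come later in the same section, from the pilot study: "the estimated risk of laryngeal injury was 0.39 for the PVC-ETT treatment group and 0.38 for the EVAC-PU-ETT treatment group".

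The timing is worded in two ways:

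- Section 10.4.2: "The analysis will be conducted when approximately 50 percent of the total sample has been collected". Section 10.4.6 repeats this sentence, and section 5.1 has nearly the same: "One interim analysis will be conducted when approximately 50 percent of the total sample has been collected".
- Section 10.4.2, shortly afterwards: "The interim analysis would take place when approximately 537 (269 patients per study arm) have been accrued".

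Section 10.1 defines the endpoint: "Safety, measured as long-term laryngeal injury, will be tested for equivalence between the two treatment groups". Section 10.4.4 assesses long-term airway sequelae by interview six months after randomization.

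**The concern.** The boundary is the only numerical interim rule in the plan, and its label tells the monitoring board how much error the look spends. At the pilot risks the number and the label disagree, and no other risk is given that would reconcile them.

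A boundary written as a fixed risk difference also keeps its meaning only at one combination of risk and number assessed. If the look is triggered by enrolment while the outcome takes six months, fewer than 537 patients contribute. The same 0.0956 is then easier to cross by chance.

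A chance stop would also cut short the quality-of-life and cognition comparisons, which are fixed-sample endpoints powered at 1,074.

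**Working it through.** **Inputs.** Boundary 0.0956, one-sided 2.5%, one look, 269 per arm, margin 0.05, pilot risks 0.39 and 0.38 (all section 10.4.2); 1,074 patients (section 10.2).

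**1. Critical values.** With looks at half and full information, the two Z statistics have correlation √0.5.
- Classical O'Brien-Fleming: c solves P(Z₁ > c√2 or Z₂ > c) = 0.025. This gives c = 1.977, interim Z = 2.797, one-sided p = 0.0026.
- Lan-DeMets O'Brien-Fleming at half information: interim Z = 2.963.

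**2. Attempt to reproduce 0.0956 at the pilot risks.** Boundary = Z × SE, with SE = √[(p₀(1−p₀) + p₁(1−p₁))/n].
- SE = √[(0.2379 + 0.2356)/269] = 0.0420.
- Classical: 2.797 × 0.0420 = 0.117. With 0.39 in both arms it is 0.118.
- Lan-DeMets: 0.124, or 0.125 with 0.39 in both arms.
- Other readings at 0.39 in both arms: Pocock 0.0916; no adjustment 0.0824; O'Brien-Fleming at one-sided 5% 0.0998; null placed at the 0.05 margin 0.1676.

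None gives 0.0956.

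**3. What 0.0956 is at risk 0.39.** Z = 0.0956/0.0421 = 2.27, one-sided p = 0.0115 (exact binomial 0.0121), against 0.0026 for the label.

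**4. Risk at which the label holds.** Solving Z × SE = 0.0956 at 269 per arm for the control risk:

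| Assumed arm difference | Classical | Lan-DeMets |
|---|---|---|
| 0 | 0.195 | 0.168 |
| 0.05 | 0.171 | 0.144 |
| 0.0956 | 0.151 | 0.124 |

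**5. Chance of a false harm stop with 537 assessed, no true difference.** It is 0.26% at risk 0.195, 0.78% at 0.30, about 1.2% at 0.39, and about 1.3% at 0.50 (1.4% exact). Since p(1−p) peaks at 0.50, that is the maximum.

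**6. If the trigger is 537 accrued.** Assume uniform accrual, the 90 patients from the first site complete, and no deaths or losses.
- 36 months (section 10.2): 984/36 × 6 = 164 not yet at six months, so 537 − 164 = 373 assessed. At risk 0.39, SE = 0.0505, Z = 1.89, p = 2.9%.
- 600 intubations a year (section 10.2) less 40% (Study Duration in section 2.1) is 30 a month, so 984 patients take 32.8 months. Then 537 − 180 = 357 assessed, Z = 1.85, p = 3.2%.
- At risk 0.195 the two figures are 1.0% and 1.1%.

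**7. Sensitivity to true harm.** With true risks 0.49 and 0.39 and 269 per arm, SE = 0.0426. The chance of stopping is 54% at 0.0956, 34% at the classical boundary and 28% at the Lan-DeMets boundary.

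**The case against.** The plan never says that 0.0956 was built from the pilot risks, or that the pilot's laryngeal injury is the same outcome as the six-month interview. A lower planning risk would make the number correct. With 537 assessed the error is bounded at about 1.3% and lies on the cautious side. The Data and Safety Monitoring Board also reviews safety by arm at least twice a year (section 11.1.6) and may recommend stopping at any time (section 11.1.2). Three of the four timing statements say *collected*, and early airway outcomes are also listed as safety endpoints.

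Most of this stands, and it rules out several stronger readings that a reader might infer:

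- *That 0.0956 is a calculation slip.* Not shown. An unstated lower risk reproduces it.
- *That the planning risk was 0.195, half the pilot's, confirmed by the power claim ("the statistical power for concluding non-inferiority of the EVAC-PU-ETT treatment group would be 80 percent").* Step 4 gives a range, not one value. Risks of 0.20 and 0.19 give 79.9% power at one-sided 5% but 69.9% at the stated 2.5%. They also need a true difference of −0.01 that the plan does not state as an assumption. A common 0.195 gives 66% and 54%. The match is too loose to identify a planning risk.
- *That a false stop could reach 12%.* This needs the *accrued* trigger and the 15-month enrolment period in section 2.1 (143 assessed). At 30 patients a month, 15 months yields 450, not 984.
- *That 0.0956 is the whole stopping decision.* It is the only stated number. Board review continues alongside it.

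None of this reconciles the number with its label at a stated risk, or says which trigger applies.

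**Conclusion.** The concern holds as a mismatch between number and label, plus an open trigger. At the pilot risks and 269 per arm, the labelled boundary is about 0.117 to 0.125, not 0.0956. The look spends about 1.2% instead of 0.26% (classical form). The plan's figure fits its label only at a control risk of roughly 0.12 to 0.20, which is not stated.

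With 537 assessed, the excess is under one percentage point. It cannot inflate false non-inferiority, because an extra harm stop only removes chances to claim it. On the *accrued* reading the chance is about 3% at risk 0.39 and about 1% at 0.195, given uniform accrual over about 33 to 36 months and no attrition. The 30-a-month rate uses 2016 counts for which section 10.2 names no hospital. If the interim outcome is an early one, the timing part falls away and the boundary part remains.

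This should be fixed before the look, but it does not undermine the trial.

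**What to change.** 1. Choose one of two forms for the boundary in section 10.4.2 and the board's charter:
   - State it on the Z scale (2.797 in the classical form at half information) or as Lan-DeMets O'Brien-Fleming spending at the actual information fraction. Convert it to a risk difference at the look from the observed risks and the number assessed.
   - Keep 0.0956 as a deliberately cautious limit, drop the 2.5% O'Brien-Fleming label, and state the error it spends (about 1.2% at risk 0.39 with 537 assessed).
2. State the planning risk and, if it differs from the pilot's, why.
3. Use one trigger wording in sections 5.1, 10.4.2 and 10.4.6, tied to the outcome used at the look. An example is the first 537 randomised reaching six months, with the boundary scaled to the number assessed. If an early airway outcome is meant, say so.

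Cost: wording in the plan and the charter. The Z-scale option stops less readily under a true 0.10 excess (34% or 28%, against 54%), so the relabelled limit is a legitimate choice. If *accrued* was meant, the look moves about six months later, with about 701 to 717 enrolled by then (537 + 164 or 537 + 180). The semiannual board reviews continue meanwhile.
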